## Revision History

Revision	Date Issued	ECO
A	10-09-2020	3308
B	12-07-2020	3363
C	03-02-2021	3440
D	04-23-2021	3519
E	05-11-2021	3548
F	03-31-2022	4103
G	06-21-2022	4285
H	08-26-2022	4452

## 1 PROTOCOL SYNOPSIS

Protocol Title	Prospective, Randomized, Masked, Controlled Trial to Evaluate the Safety and Effectiveness of the TearCare® System in the Treatment of the Signs and Symptoms of Dry Eye Disease (SAHARA)
Protocol ID Number	07093
Study Device	TearCare® System
Control Group	Restasis® (0.05% Cyclosporine ophthalmic emulsion)
Primary Objective	To demonstrate the safety and effectiveness of TearCare® procedures compared to Restasis® to treat the signs and symptoms of dry eye disease in adult patients.
Study Design	Prospective, randomized, masked, multi-center, superiority, non-significant risk study.
Primary Effectiveness Endpoint	
Mean Change from baseline in:
 
 
○ Tear Break-Up Time (TBUT)
 
○ Ocular Surface Disease Index (OSDI) score
 
 
Superiority will be assessed at 6 month

Secondary Effectiveness Endpoints	
Mean Change from baseline in:
 
 
○ Total Meibomian Gland Secretion Score
 
○ Corneal staining scores
 
○ Conjunctival staining scores
 
○ Number of Meibomian Glands Yielding any liquid
 
○ Number of Meibomian Glands Yielding clear liquid
 
○ Symptom Assessment in Dry Eye (SANDE) scores
 
○ Eye Dryness Score
 
○ Schirmer score
 
○ Ocular protection index (OPI): Interblink interval (IBI)/TBUT
 

Primary Safety Endpoint	
 
○ Procedure (TearCare)/Treatment (Restasis)-related adverse events
 

Secondary Safety Endpoints	
 
○ Change in best corrected visual acuity (ETDRS)
 
○ Change in intraocular pressure (IOP)
 

**Inclusion Criteria**

1. At least 22 years of age
2. Reports dry eye symptoms within the past 3 to 6 months
3. Reports having to use artificial tears or lubricants regularly over the past month to relieve dry eye symptoms.
4. Schirmer tear test (with anesthesia)  $\geq 5$  to  $\leq 15$  mm in 5 minutes
5. OSDI Score of 23-79
6. TBUT of  $\geq 1$  to  $\leq 7$  seconds in both eyes
7. Meibomian gland obstruction in both eyes based on a total Meibomian Gland Secretion Score  $\leq 12$  in each eye.
8. At least 15 glands in each lower eyelid should be expressible, with a sterile cotton swab, at the slit lamp.
9. Best corrected visual acuity of 20/100 or better in both eyes.
10. Willing and able to comply with the study procedures and follow-up
11. Willing and able to provide informed consent
12. English-speaking

Exclusion Criteria	

1. Use of any of the following medications:

a) Cyclosporine (Restasis, Cequa etc.) or Xiidra and serum tears within 60 days prior to baseline;

b) Antihistamines (oral or topical) within 7 days prior to baseline.

c) Systemic medication(s) that is known to cause ocular dryness (e.g., diuretics, anti- hypertensives, anti-depressants, antihistamines, hormone therapy) and whose dose of this medication(s) has not been stable within 30 days prior to baseline. There must be no anticipated adjustments to the dose of these medications for the duration of the trial.

d) Accutane (at any time);

e) Oral tetracyclines or azithromycin within 30 days prior to baseline; or

f) Topical ophthalmic antibiotics, anti-glaucoma medications, steroids, non-steroidal anti-inflammatory medications within 30 days prior to baseline.

2. Any of the following dry eye treatments:

a) Office-based dry eye treatment (e.g. IPL, TearCare, thermal pulsation [LipiFlow], iLux etc.) within 12 months prior to baseline either as part of routine care or clinical investigation;

b) Planned or recent surgical procedures to the eye or eyelid (90 days prior to baseline)

c) Meibomian gland expression within 6 months prior to baseline;

d) Blephex or debridement within 3 months prior to baseline is an exclusion;

e) Punctal occlusion or punctal plugs. Investigators can choose to remove the punctal plugs 15 days prior to baseline;

f) Use of tear neurostimulators (i.e., True Tear, iTear100, Tyrvaya) within 2 weeks of the baseline visit. (Subjects must refrain from using tear neurostimulators for the duration of the study.); or

g) Any history of meibomian gland probing

3. History of eyelid, conjunctiva, or corneal surgery (including refractive surgery) within the past year prior to baseline. In addition, subjects with any history of the following are excluded: chalazion surgery, surgery on the tarsal conjunctiva, radial keratotomy (RK), complicated blepharoplasty, lid reconstruction, or significant complications post-refractive surgery.

4. Contact lens use within 2 weeks of the baseline visit.

5. Active hordeolum, stye, or chalazion at the time of the baseline visit.

6. History of Herpes Simplex or Herpes Zoster of the eye or eyelid.

7. Any active, clinically significant ocular or peri-ocular infection, inflammation, or irritation.

---------------------------	--

8. Recurrent clinically significant eye inflammation, other than dry eye, within 3 months prior to baseline.
9. Clinically significant anterior blepharitis. In addition, collarettes or flakes of more than one quarter of the eyelid are excluded.
10. Clinically significant eyelid abnormalities in either eye (e.g. entropion/ectropion, blepharospasm, aponeurotic ptosis, lagophthalmos, distichiasis, trichiasis).
11. Clinically significant dermatologic or cutaneous disease of the eyelid or periocular area.
12. In the clinical judgement of the investigator, meibomian glands have significant capping, atrophy, or are unable to be expressed, digitally or with a sterile cotton swab.
13. Clinically significant ocular surface abnormalities that may affect tear film distribution or treatment (e.g., pterygium, anterior membrane dystrophy, Salzmann's nodules, etc.)
14. Corneal surface abnormalities such as corneal epithelial defects (other than punctate staining), ulcers, corneal epithelial dystrophies, keratoconus, and ectatic disease of the cornea
15. Any active, clinically significant allergic, vernal, or giant papillary conjunctivitis.
16. Ocular trauma within 3 months prior to baseline.
17. Known history of diminished or abnormal facial, periocular, ocular or corneal sensation
18. Systemic diseases resulting in dry eye (e.g. autoimmune diseases such as Sjogren's syndrome, rheumatoid arthritis, lupus, Graves' disease, sarcoidosis, etc.)
19. Subject is currently using Retin A /Retin A derivatives.
20. Subject has permanent eyeliner/lid tattoos, eyelash extensions or wears false eyelashes.
21. Subject is currently using Latisse, Lash Boost or any other type of eyelash growth serum.
22. Allergies to silicone tissue adhesives, acrylates and/or copper.
23. Subject has a pacemaker or implantable cardiac defibrillators (ICD).
24. Participation in another ophthalmic clinical trial 30 days prior to baseline. Subject must also be willing to refrain from another ophthalmic study for the duration of the study.
25. Co-existing condition, either ocular or non-ocular that, in the judgement of the investigator could affect the safety or effectiveness of treatment or the compliance of the subject to the protocol. For example, subjects who are pregnant or nursing or have active, wet macular degeneration are excluded.

Number of Subjects Enrolled	Approximately 412 enrolled
Randomization	1:1
Number of Centers	Up to 25
Study Duration for Each Subject	Up to 24 months
Total Study Duration	Approximately 40 to 50 months
Schedule of Visits	
TearCare group (Study Device):
 
Baseline, Procedure Day 0, Day 1, Week 1, Month 1, Month 3, Month 5, Month 6, Month 9, Month 12, Month 15, Month 18, Month 24
 
TearCare procedure will be given within 7 days of Baseline and at 5 Months. Beginning at 9 Months, subjects will receive an additional TearCare procedure when TBUT drops lower than Baseline or within 2 seconds of baseline AND if OSDI worsens by at least 15 points compared to the previous visit*.
 
(*Based on the recommended cutoffs for OSDI Total score, the severity of the subject's dry eye symptoms is categorized as; Normal – 0-1, Mild – 13-22, Moderate – 23-32, Severe – 33 or higher)
 
Restasis group (Control):
 
Baseline, Restasis Day 0, Day 1, Week 1, Month 1, Month 3, Month 6
 
Subjects will be required to self-administer 1 drop twice a day from baseline through the Month 6 visit. At Month 6, subjects from the Restasis group will be crossed over to the TearCare group and will receive one (1) TearCare procedure and will be followed as below:
 
Day 1, Week 1, Month 1, Month 9, Month 12

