## 9 STUDY PROCEDURES

### 9.1 TABLE 3: TEARCARE STUDY VISIT SCHEDULE

Visit	Baseline	Day 0 b	Day 1	Wk 1	1 M	3 M	5 M	6 M	9 M	12 M	15 M	18 M	24M
Window days	-7 to 0	0	1	5-9	21-35	70-100	120-155	170-210	250-300	330-390	420-480	510-570	691-780
Informed Consent	X a												
Demographics, Ocular & Medical History	X												
Medication use	X			X	X	X		X	X	X	X	X	X
Questionnaires (OSDI, SANDE, Eye Dryness Score)	X			X	X	X		X	X	X	X	X	X
BCVA d	X		X e	X e	X	X		X	X	X	X	X	X
Blink rate	X			X				X		X			X
Slit Lamp Exam	X		X	X	X	X		X	X	X	X	X	X
TBUT	X			X	X	X		X	X	X	X	X	X
Corneal Staining	X			X	X	X		X	X	X	X	X	X
Conjunctival Staining	X			X	X	X		X	X	X	X	X	X
Schirmer Test	X			X	X			X		X			X
MGSS	X			X	X	X		X	X	X	X	X	X
IOP f	X		X	X	X	X		X	X	X	X	X	X
Subject Eligibility	X												
Randomization	X												
TearCare Procedure		X					X						
AE Assessment	X	X	X	X	X	X	X	X	X	X	X	X	X
Eye Lubricant/Drop Log				X	X	X	X	X	X	X	X	X	X

a Subjects may sign the informed consent up to 60 days in advance of the baseline visit.

b TearCare procedure must be performed within 7 calendar days of the Baseline visit. If scheduling permits, it may be performed on the same day as the Baseline visit following Randomization. Beginning at 9 Months, subjects will receive an additional TearCare procedure when TBUT drops lower than Baseline or within 2 seconds of baseline AND ifOSDI worsens by at least 15 points compared to the previous visit.

d BCVA should be collected after manifest refraction using ETDRS visual acuity chart

e On Day 1 and Week 1, Best Corrected Spectacle Visual Acuity (BCSVA using ETDRS) is measured without manifest refraction (MR). If the VA has worsened by  $\geq 10$  letters (per ETDRS) from baseline, then MR should be performed, the ETDRS measurement should be repeated, and the VA post-MR should be recorded.

f IOP measured via applanation tonometry should be measured at baseline using standard of practice at each site with the same method to be used for all consecutive visits in the study.

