#### **9.6.5 RESTASIS DISTRIBUTION (CONTROL GROUP)**

Subjects randomized to the control group (Restasis) will be provided with Restasis® (Cyclosporine 0.05% ophthalmic emulsion) for use in both eyes. Subjects should be instructed to follow steps below while administering Restasis:

Preparing the bottle for first-time use:

- a. Pull off shipping cover by pulling straight up. Remove the pull tab on the olive green colored protective cap by pulling the end of the pull tab away from the bottle then winding it counterclockwise.
- b. Remove the olive green colored protective cap by pulling it straight up. Keep the colored protective cap. Prime the bottle for first time use by squeezing 2 drops onto a tissue. Do not let the bottle tip touch the tissue.
- c. After use, recap the bottle with the olive green colored protective cap by pushing straight down onto the bottle.
- d. Turn the bottle upside down a few times before putting drops in eyes to make sure the medicine is mixed well.
- e. Instill one drop in both eyes approximately 12 hours apart from each other. The first drop should be instilled between 7 to 8 AM and second drop between 7 to 8 PM.
- f. Do not discontinue use of medication unless instructed by the site staff.

The site staff should give intermittent calls to the subjects to check if they have enough supply of the drops that last until their next visit. Please instruct subjects to inform the site staff before they run out of the medication. Each subject will receive the first bottle on Day 0 (treatment day). All additional bottles of Restasis will be provided at the protocol defined follow-up visits (Week 1, Month 1, and Month 3). To avoid shortage of medication, please try to bring the subject in at the early part of the visit window. If this requires scheduling an additional visit in between the protocol defined visits, it will be

---

considered an unscheduled visit.

The subjects should be instructed to:

- a. Store Restasis® between 15-25 °C (59-77 °F)
- b. For contact lens wearers, drops should be instilled at least 15 minutes after the removal of the contact lenses.
- c. Restasis® can be used with lubricant eye drops, but you should wait at least 15 minutes between using each product. The lubricant eye drops/rescue drops used should be recorded on the Eye Lubricant/Drop log. Sites should make sure to review the log at each visit as described in Section 9.6.6.

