### **12.6.4 SAFETY ANALYSIS**

All adverse events will be reported by study group and AE category. Any serious adverse events will be completely described in the study report. The primary safety endpoint will be summarized for each study group.

We will compute the incidence of ocular events in two ways: first as a simple proportion, counting the number of subjects with any event (that is, counting the first event per person in either eye), then as an incidence rate, counting all events including repeated events per subject.

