## **22.6 SAFETY ANALYSIS**

All adverse events will be reported by treatment group and AE category. Any serious adverse events will be completely described in the study report. The primary safety endpoint will be summarized for each treatment group.

We will compute the incidence of ocular events in two ways: first as a simple proportion, counting the number of subjects with any event (that is, counting the first event per person in either eye), then as an incidence rate, counting all events including repeated events per subject.

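### The primary objective promises safety compared with Restasis, but no between-arm safety estimate is planned for the randomised period, and adverse-event ascertainment to Month 6 differs by arm

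*Combined protocol and SAP*

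**What the plan says.** The primary objective in Section 1 is "To demonstrate the safety and effectiveness of TearCare® procedures compared to Restasis® to treat the signs and symptoms of dry eye disease in adult patients". Sections 6.2 and 12.6.2 define the primary safety endpoint as the incidence of procedure-related (TearCare) or treatment-related (Restasis) AEs.

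On analysis, Section 12.6.4 says "The primary safety endpoint will be summarized for each study group" and Section 22.6 says "The primary safety endpoint will be summarized for each treatment group". Both add a simple proportion of subjects with any ocular event and an incidence rate counting repeat events. Section 12.6.1 tabulates AEs by visit and group. The hypotheses in Sections 12.5.3 and 22.2 concern TBUT and OSDI only. The one safety precision statement, Section 22.4.2, covers the TearCare arm alone at 24 months. Under Section 7.1 controls receive a TearCare procedure at Month 6.

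On ascertainment, the synopsis lists TearCare visits as "Baseline, Procedure Day 0, Day 1, Week 1, Month 1, Month 3, Month 5, Month 6" and onward, and Restasis visits as "Baseline, Restasis Day 0, Day 1, Week 1, Month 1, Month 3, Month 6". Tables 3 and 4 mark an AE assessment in every column, but Table 4 has no Month 5 column. Between Months 3 and 6 the other control contacts described are supply calls (Section 9.6.5: "The site staff should give intermittent calls to the subjects to check if they have enough supply of the drops") and, if supply requires it, an unscheduled visit. No AE question is attached to either.

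**The concern.** The randomised safety comparison exists only until Month 6, because controls then receive the study device. That is the period for which a difference between the arms would be interpretable, and the plan fixes no estimate, interval or cut-off for it. After Month 6 the safety population is analysed as treated, and there is no rule for where a control subject's post-crossover events are counted.

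A reader who subtracts the two reported incidences would also be comparing arms that were questioned a different number of times and followed to different days. At stake is the safety half of the primary objective. The effectiveness conclusions are not affected.

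**Working it through.** **The plan's own safety figure.** Section 22.4.2 gives margins of 4.4%, 6.0% and 8.1% for AE rates of 5%, 10% and 20% with n = 98. The plain formula 1.96 × √(p(1−p)/98) gives 4.32, 5.94 and 7.92. Using the t quantile with 97 degrees of freedom (1.985) and divisor 97 gives 4.39, 6.05 and 8.06, which matches. The 98 follows from 150 × 0.9⁴ = 98.4. These margins describe one arm at 24 months, so they say nothing about a difference from Restasis.

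**AE assessments after Day 0, up to and including Month 6 (Tables 3 and 4).**
- TearCare: Day 1, Week 1, Months 1, 3, 5, 6 = 6.
- Restasis: Day 1, Week 1, Months 1, 3, 6 = 5.

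**Gaps after Month 3, from the window rows.**
- Restasis, Month 3 (70-90) to Month 6 (150-180): 150 − 90 = 60 to 180 − 70 = 110 days; midpoints 165 − 80 = 85.
- TearCare, Month 3 (70-100) to Month 5 (120-155): 20 to 85 days; midpoints 137.5 − 85 = 52.5.
- TearCare, Month 5 to Month 6 (170-210): 15 to 90 days; midpoints 190 − 137.5 = 52.5.

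**Time at risk to Month 6.** Midpoints 190 and 165 days: 190/165 = 1.15. With equal constant hazards, a 10% incidence by day 165 becomes 1 − 0.9^(190/165) = 11.4% by day 190. For 5% and 20% the figures are 5.7% and 22.7%. This arises even if every event is recalled.

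**Illustration of recall (assumptions, not document figures).** Suppose true event rates are equal and constant, and an event is recorded only if it fell within r days before a contact. Contacts are at window midpoints: TearCare days 1, 7, 28, 85, 137.5, 190; Restasis days 1, 7, 28, 80, 165. The last column adds a Restasis contact at day 137.5.

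| r (days) | TearCare days covered | Restasis days covered | Ratio | Ratio with added contact |
|---|---|---|---|---|
| 14 | 63 | 49 | 1.29 | 63/63 = 1.00 |
| 30 | 118 | 88 | 1.34 | 118/115.5 = 1.02 |
| 45 | 163 | 118 | 1.38 | 163/145.5 = 1.12 |
| 60 | 190 | 140 | 1.36 | 190/165 = 1.15 |
| unlimited | 190 | 165 | 1.15 | 190/165 = 1.15 |

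A Month 5 contact alone therefore does not equalise the arms unless recall is short. A common cut-off day is needed.

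**Precision of a planned difference.** Section 22.4.1 expects 139 per arm at Month 6. The Wald half-width for equal rates is 1.96 × √(2p(1−p)/n). The Newcombe half-width is √((p−l)² + (u−p)²), with l and u the single-arm Wilson limits.

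| Rate | Wald, n = 139 | Newcombe, n = 139 | Wald, n = 155 |
|---|---|---|---|
| 5% | 5.1 | 5.6 | 4.9 |
| 10% | 7.1 | 7.3 | 6.7 |
| 20% | 9.4 | 9.4 | 8.9 |

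Figures are percentage points. The 155 is the August 2022 target in Section 12.7 less dropout: 175 × 0.89 = 155.75.

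**The case against.** Descriptive safety reporting is a legitimate choice. Section 2 speaks of evaluating rather than demonstrating, no safety hypothesis is stated, and group incidences will appear side by side, so a reader can form a crude difference. This stands to the extent that the plan is not silent on safety, and it would be too strong to say that the report could tell a reader nothing. It does not supply an interval, a period or a rule at crossover, and the synopsis does say *demonstrate* and *compared*.

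The unequal schedule is a gap in prompting, not in coverage. Section 10 requires ocular AEs to be documented throughout the trial, and controls have an AE assessment at Month 6. The proportion also counts each subject once, so controls already counted by Month 3 are unaffected. This stands: what may be lost is recall of events in the gap, and the covered-days ratios above do not measure bias in that proportion.

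Two stronger readings are tempting. One is that the extra Month 5 question biases the comparison against TearCare. The documents do not settle this. Month 5 is itself a procedure visit, and Table 3 has no Day 1 or Week 1 check after it, so short-lived events following that procedure may be under-recorded in the TearCare arm. The other is that a Month 5 control contact would make the comparison fair. It would not, because the Month 6 windows would still differ.

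**Conclusion.** The point holds. The comparative safety aim has no planned between-arm estimate, and no analysis is confined to the randomised period before crossover. Ascertainment to Month 6 differs in two documented ways: 6 against 5 AE assessments after Day 0, and about 15% more TearCare time at risk at mid-window. The size of the resulting bias cannot be derived from the documents. Any figure needs assumptions about recall and event timing, and the net direction is uncertain.

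The estimate is feasible but of modest precision: half-widths of about 5 to 9 points with 139 per arm, assuming equal rates of 5% to 20%. This is an inexpensive improvement to the safety analysis and not a flaw in the effectiveness conclusions.

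**What to change.** **1. Sections 12.6.4 and 22.6 (main change).** Prespecify the TearCare-minus-Restasis difference in the proportion of subjects with at least one related AE, and separately with any ocular AE, each with a Newcombe 95% interval. Count events by onset date from Day 0 to a common cut-off day in both arms, and before any crossover procedure. Day 150, the start of the Restasis Month 6 window, is one candidate. Add exposure-adjusted rates, with control person-time censored at crossover and TearCare person-time ending at the Month 6 visit. These rates matter because a day-150 cut-off leaves at most 30 days after a Month 5 procedure (window 120-155), and none if it is done on or after day 150.

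If no comparison is intended, change the synopsis objective so that safety is described rather than demonstrated against Restasis.

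The cost is a short paragraph in each section. Event dates are already recorded (Sections 10 and 10.3). One point to check: those sections name only the relationship to the study device, so the related-AE difference requires that relationship to Restasis is recorded as well. The any-ocular-AE difference does not depend on this.

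**2. Table 4 and Section 9.6.5 (optional, prospective only).** For controls not yet past Month 5, add the standard AE question to a supply call at days 120-155, and report how many controls were asked. The cost is one scripted question in a type of call the protocol already asks sites to make. The drawback is a mix of prompted and unprompted controls: subjects had already been treated by May 2021 (Section 12.7) and the current revision dates from August 2022, so some controls are probably past that point.

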## 2 STUDY OBJECTIVE

The objective of this study is to evaluate the safety and effectiveness of TearCare® procedures when compared Restasis® to treat the signs and symptoms of dry eye disease in adult patients.

## 3 BACKGROUND AND JUSTIFICATION FOR THE STUDY

Dry Eye Disease (DED) is a chronic eye condition that can cause an array of symptoms in patients, ranging from periodic ocular discomfort to severe corneal inflammation,

scarring, and vision loss. Approximately 1/3 of patients visiting their eye doctor suffer from dry eye. The prevalence of dry eye disease increases with age, especially in postmenopausal women. It is estimated that dry eye disease affects more than 7 million Americans older 40 years of age, and approximately 1 million to 4 million Americans between 65 to 84 years of age.

Each year in the U.S., billions of dollars are spent on topical lubricants, medications, tear duct occlusions, and other treatments to control the chronic condition of dry eye disease. Yu et al reported that the average annual cost of managing a patient with dry eye was \$783 (range \$757 – 809) from the payers' perspective. When adjusted to the prevalence of DED nationwide, the overall burden of DED on the US healthcare system was estimated to be \$3.84 billion. Moreover, there is a great cost to society in terms of decreased productivity due to the symptoms of dry eye. Yu, et al estimated the societal cost to be \$11,302 per patient and \$55.4 billion to the US society overall. Essentially, not only do dry eye patients directly suffer, but there is also a burden to healthcare, employers, and society.

Historically, dry eye disease has been categorized into one of two forms, aqueous tear deficiency and evaporative tear deficiency. The current understanding is that evaporative dry eye is more common than aqueous deficient dry eye. However, because the symptoms of aqueous-deficient dry eye are difficult to differentiate from those of evaporative dry eye, it is often impossible to truly separate patients into distinct groups. In fact, AAO guidelines state that these conditions coexist in the majority of the patients with the disease.

In terms of the mechanism of action for dry eye disease, the International Dry Eye Workshop (DEWS) explained that tear hyperosmolarity and the symptoms of dry eye result from water evaporation caused by low aqueous tear flow and/or excessive evaporation. This reduced, concentrated tear volume, in turn results in further inflammation and tear film instability creating a vicious cycle. The DEWS report

---

